Study design		Using a traditional "3+3" dose-escalation design, subjects will be sequentially assigned to one of three dose groups (2.8×10^{10} units, 1.4×10^{11} units, and 7.0×10^{11} units per dose, once daily, with continuous intranasal instillation for 4 days). Each dose group will include 3 subjects, who will be enrolled one by one. The exploration of the next dose can only proceed if no dose-limiting toxicity (DLT) is observed in the 3 subjects. If 1 out of the 3 subjects experiences DLT, an additional 3 subjects will be enrolled in the same dose group; the exploration of the next dose can only move forward if no DLT is observed in these newly added 3 subjects. A minimum of 6 and a maximum of 18 subjects will be recruited during the dose exploration phase. Patients will receive other standard medical treatments in accordance with the recommendations in the 2022 Chinese Guidelines for Secondary Prevention of Ischemic Stroke and Transient Ischemic Attack , including antiplatelet drugs or anticoagulants, antihypertensive drugs, lipid-lowering drugs, and glucose-lowering drugs.
Outcome Measures	Primary Outcome Measure	Dose-Limiting Toxicity (DLT) Related to hUC-MSC-sEV-001 Includes: (1) Grade 3-4 severe adverse events occurring on day 14 (+-2), graded according to Common Terminology Criteria for Adverse Events (CTCAE) V5.0; (2) NIHSS score increase of ≥ 4 from baseline on day 14 (+-2); NIHSS score assessed by a professional rehabilitation physician;(3) Symptomatic intracranial hemorrhage occurring on day 14 (+-2); detected via CT scan and patient symptom presentation.
	Secondary Outcome Measures:	Serious adverse events related to the investigational drug within 90 (+-7) days. Distribution of Modified Rankin Scale (mRS) Scores within 90 (+-7) days. Barthel Index within 90 (± 7) days. Five-level, five-dimensional EuroQol (EQ-5D-5L) . Proportion of Modified Rankin Scale (mRS) Scores of 0-2 within 90 (+-7) days. All-cause mortality at 90 (+-7) days. Changes in infarct volume at 14 (+-2) days compared to baseline. Change from Baseline in National Institutes of Health Stroke Scale (NIHSS) Score.
Follow-up duration		Baseline (0~1 day), 7 (± 1) days, 14 (± 2) days, 90 (± 7) days
Sample size		6-18 subjects need to be included.

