1. Neurological Function Scales:

- **NIHSS:** Assesses the severity of neurological deficits (range: 0-42; higher scores indicate more severe deficits). Administered at baseline, Day 7, Day 14, and Day 90.
- **mRS:** Assesses functional independence (range: 0-6; scores 0-2 indicate good functional outcome). Administered at baseline, Day 7, Day 14, and Day 90.
- **Modified Barthel Index (MBI):** Assesses activities of daily living (range: 0-100; higher scores indicate better independence). Administered at baseline, Day 14, and Day 90.
- **EQ-5D-5L:** Assesses health-related quality of life (including mobility, self-care, usual activities, pain/discomfort, anxiety/depression; scored as a utility value ranging from -0.291 to 1.0). Administered at baseline, Day 14, and Day 90.

2. Cerebral Perfusion Parameters (CTP):

- Measured at baseline, Day 14, and Day 90: cerebral blood volume (CBV), cerebral blood flow (CBF), mean transit time (MTT), time to peak (TTP) in the infarct core and penumbra.
- Changes in perfusion parameters from baseline are used to evaluate the improvement of cerebral blood flow.

3. Infarct Volume Measurement:

- Infarct volume is measured on DWI using the ABC/2 method (A: maximum length, B: maximum width perpendicular to A, C: number of slices × slice thickness).
- Changes in infarct volume from baseline to Day 14 are used to evaluate infarct progression or regression.

5. Outcome Evaluation Indicators

(1) Primary Safety Endpoints

- **Dose-Limiting Toxicity (DLT):** Assessed within 14 days of the first dose, defined as any of the following:
 1. Grade 3-4 AE related to the study drug (CTCAE V5.0), such as severe nasal bleeding, anaphylactic reaction, or hepatic injury;
 2. Increase in NIHSS score ≥ 4 points from baseline (indicating significant neurological deterioration);
 3. Symptomatic intracranial hemorrhage (confirmed by CT/MRI and associated with neurological deterioration).

(2) Secondary Safety Endpoints

1. **SAE Incidence:** Proportion of subjects with drug-related SAEs within 90 days of the first dose;
2. **All-Cause Mortality:** Proportion of subjects who die from any cause within 90 days of the first dose;
3. **Laboratory Abnormality Rate:** Proportion of subjects with Grade ≥ 3 laboratory abnormalities (e.g., thrombocytopenia, elevated liver enzymes) within 90 days.

(3) Efficacy Endpoints

1. **Functional Outcome:** Proportion of subjects with mRS score 0-2 at Day 90;

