
- **Recovery Procedures:**

1. The CRC labels the recoverable study drug with "To Be Recovered" and records the reason in the inventory log;
2. The study drug is returned to the sponsor in insulated containers with dry ice, accompanied by a "Study Drug Recovery Form";
3. The sponsor confirms receipt and issues a "Recovery Confirmation Certificate", which is stored in the study file.

8. Observation and Management of Adverse Events

(1) Definitions

- **Adverse Event (AE):** Any untoward medical occurrence in a subject administered a pharmaceutical product, which does not necessarily have a causal relationship with this treatment. AEs include clinical signs (e.g., abnormal laboratory findings), symptoms, or diseases.
- **Serious Adverse Event (SAE):** An AE that results in death, is life-threatening, requires inpatient hospitalization or prolongation of existing hospitalization, causes persistent or significant disability/incapacity, or is a congenital anomaly/birth defect.
- **Adverse Drug Reaction (ADR):** A response to a drug that is noxious and unintended, and which occurs at doses normally used in humans for the prophylaxis, diagnosis, or therapy of diseases, or for the modification of physiological function.
- **Dose-Limiting Toxicity (DLT):** An AE that is severe enough to prevent dose escalation, as defined in Section 5.1 (Primary Safety Endpoints).

(2) Observation and Recording of Adverse Events

- **Monitoring Period:** From the time of informed consent signing until 30 days after the last dose of the study drug.
- **Reporting Requirements:** Subjects are instructed to report any new symptoms, signs, or discomfort to the investigator immediately. The investigator queries the subject about AEs at each visit using open-ended questions (e.g., "Have you experienced any new symptoms since your last visit?").
- **Documentation:** All AEs are recorded in the "Adverse Event Record Form" in the CRF, including:
 - Onset time, date, and duration;

- Severity (CTCAE V5.0: Grade 1 = mild, Grade 2 = moderate, Grade 3 = severe, Grade 4 = life-threatening, Grade 5 = death);
- Description of signs and symptoms (e.g., "nasal congestion, mild, lasting 2 days");
- Relationship to the study drug (assessed using the five-point scale: definite, probable, possible, unlikely, unrelated);
- Treatment measures (e.g., "normal saline nasal irrigation");
- Outcome (resolved, resolving, stable, worsening, fatal).

(3) Management of Adverse Events

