- **Source Documents:** Medical records, laboratory reports, imaging films, and informed consent forms are stored in the hospital's medical record department or study office for 30 years after study completion.
- **Electronic Data:** The EDC database and backup files are stored on a secure server with restricted access. The data are retained for 30 years after study completion.
- **Statistical Analysis Data:** The locked database and statistical analysis code are stored in a secure location and retained for 30 years after study completion.

11. Statistical Analysis

(1) Statistical Analysis Sets

- **Full Analysis Set (FAS):** Includes all randomized subjects who receive at least one dose of the study drug. Missing efficacy data are imputed using the last observation carried forward (LOCF) method.
- **Per Protocol Set (PPS):** Includes subjects in the FAS who comply with the study protocol (e.g., complete all visits, receive all 4 doses of study drug, no major protocol violations). This set is used for sensitivity analysis of efficacy outcomes.
- **Safety Analysis Set (SAS):** Includes all subjects who receive at least one dose of the study drug. This set is used for safety analyses (adverse events, laboratory abnormalities).

(2) Descriptive Statistics

- **Continuous Variables:** Presented as mean \pm standard deviation (SD) for normally distributed data, or

median (P25, P75) for non-normally distributed data. Examples include age, NIHSS score, and infarct volume.

- **Categorical Variables:** Presented as frequency (percentage). Examples include gender, hypertension status, and mRS score categories (0-2 vs. 3-6).

(3) Inferential Statistics

- **Primary Efficacy Endpoint:** The proportion of subjects with mRS score 0-2 at Day 90 is compared between dose groups using the chi-square test or Fisher's exact test. A generalized linear model is used to adjust for potential confounders (e.g., age, baseline NIHSS score).
- **Secondary Efficacy Endpoints:**
 - Mean changes in NIHSS, MBI, and EQ-5D-5L scores from baseline are compared using repeated measures analysis of variance (ANOVA) or Kruskal-Wallis rank sum test.
 - The proportion of subjects with NIHSS score reduction ≥ 4 points at Day 14 is compared using the chi-square test.
- **Safety Endpoints:**
 - The incidence of AEs and SAEs is compared between dose groups using the chi-square test or Fisher's exact test.

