- **Laboratory Certification:** All laboratory tests are performed by a certified clinical laboratory (accredited by the College of American Pathologists [CAP] or the National Center for Clinical Laboratories [NCCL] of China).
- **Quality Control Samples:** The laboratory runs internal quality control samples (e.g., normal and abnormal controls for CBC) with each batch of tests to ensure accuracy. External quality assessment (EQA) is participated in to verify test reliability.
- **Reference Ranges:** Laboratory reference ranges are documented in the CRF and EDC system to ensure consistent interpretation of results.

(4) Monitoring and Audit

- **Monitor Visits:** The monitor conducts site visits every 4 weeks to review subject recruitment, data entry, SDV, and adverse event reporting. A monitoring report is submitted after each visit.
- **Audit:** The sponsor conducts a formal audit of the study site 6 months after study initiation to assess protocol compliance, data integrity, and ethical compliance. The audit results are documented in the "Audit Report".
- **Regulatory Inspection:** The NMPA may conduct an inspection of the study site to verify compliance

with GCP and regulatory requirements.

(5) Quality Assurance Statement

The principal investigator is responsible for the overall quality of the study. A quality assurance plan is developed to ensure that all study activities are conducted in accordance with the protocol, GCP, and regulatory requirements. Any quality issues are documented, investigated, and corrected in a timely manner.

13. Study Reporting

(1) Interim Reports

- Interim reports are submitted to the Ethics Committee and sponsor every 6 months, summarizing subject recruitment, adverse events, protocol deviations, and preliminary safety data.
- The interim report includes a safety overview (incidence of AEs/SAEs, DLT cases) and an update on study progress (number of subjects enrolled, number of subjects completing the Day 90 visit).

(2) Final Study Report

- The final study report is prepared by the principal investigator and statistician within 6 months of study completion. The report includes:
 - Executive summary;
 - Study background and objectives;
 - Study design and methods;
 - Subject demographics and baseline characteristics;
 - Safety results (AE/SAE incidence, DLT, laboratory abnormalities);
 - Efficacy results (functional outcomes, neurological improvement);

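### The SAE endpoint counts only drug-related SAEs, but the stated analysis compares SAEs regardless of cause, and no cut-off for relatedness is given for this endpoint

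*Protocol*

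**What the plan says.** **Endpoint.** Section 5(2), item 1, under the label SAE Incidence: "Proportion of subjects with drug-related SAEs within 90 days of the first dose". The synopsis lists the same quantity among the secondary outcomes: "Serious adverse events related to the investigational drug within 90 (+-7) days".

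**Analysis.** Section 11(3), Safety Endpoints: "The incidence of AEs and SAEs is compared between dose groups using the chi-square test or Fisher's exact test". No line in section 11 names the drug-related SAE proportion.

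**Reporting.** Section 13(2) lists, for the final report, "Safety results (AE/SAE incidence, DLT, laboratory abnormalities". Section 13(1) says of the interim reports: "The interim report includes a safety overview (incidence of AEs/SAEs, DLT cases". Neither carries a causality qualifier.

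**Definitions.** Section 8(1) describes an AE as an occurrence "which does not necessarily have a causal relationship with this treatment", and an SAE as an AE that meets a seriousness criterion. Under section 8(2), causality is "assessed using the five-point scale: definite, probable, possible, unlikely, unrelated".

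**Neighbouring endpoints.** The primary safety endpoint in section 5(1) is DLT: "Assessed within 14 days of the first dose, defined as any of the following". There, item 1 is limited to drug-related events, while items 2 (NIHSS rise) and 3 (symptomatic intracranial hemorrhage) carry no causality condition. Section 5(2) also has all-cause mortality and Grade 3 or higher laboratory abnormalities, each to 90 days.

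**Collection window.** Sections 4(2), 6 (Fourth Visit) and 8(2) end AE monitoring 30 days past the final dose. The visit table in section 6 still marks AE recording at Day 90.

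**The concern.** An SAE judged unrelated counts in the quantity that section 11(3) compares, but not in the endpoint that section 5(2) pre-specifies. This leaves two readings. If section 11(3) is taken literally, the pre-specified endpoint has no stated analysis. If the section 5(2) label governs what SAE incidence means throughout, non-fatal SAEs of any cause are not analysed as such.

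The causality filter is also weak in this design. No control group and no blinding are described, and doses are filled in sequence. The attributing investigator therefore knows that every subject received drug, and at which dose. The events of most interest in these patients (hemorrhage, neurological worsening, pneumonia) are ones the stroke itself can produce. A related-only count can lose drug harm that takes this form, and attribution habits may change as the trial moves up the doses.

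**Working it through.** The protocol gives no SAE rate and bases no sample size on one, so there is no stated figure to reproduce. The check is a comparison of texts followed by an illustration.

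**1. Does the analysis match the endpoint?**

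| Place | Quantity | Causality | Window |
|---|---|---|---|
| Synopsis, secondary outcomes | SAEs | drug-related | 90 (±7) days |
| 5(2) item 1 | subjects with SAEs | drug-related | 90 days from first dose |
| 11(3) | AEs and SAEs, compared by dose | none stated | none stated |
| 13(1), 13(2) | AE/SAE incidence, listed | none stated | none stated |
| 8(1) | definition of AE and SAE | irrespective of cause | – |

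The defining places agree with each other. The mismatch is between them and section 11(3). The any-cause reading of 11(3) comes from the definitions in 8(1); section 11(3) does not itself use those words.

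**2. What can the causality scale in section 8(4) deliver?** It counts supporting factors out of five: timing, known effects, dechallenge, rechallenge, and absence of another explanation.

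- Rechallenge is declared not applicable. At most 5 − 1 = 4 factors can support causality. Definite needs five, so it cannot be reached.
- Probable needs four, so all four remaining factors must support causality.
- An event the stroke could explain also loses the alternative-etiology factor: 4 − 1 = 3 at most, which is Possible. If it also lies outside the known profile of the product, 3 − 1 = 2, which is Unlikely.
- Dosing runs from Day 0 to Day 3 (section 3(2)). For an event starting later, dechallenge is uninformative because dosing has ended: 4 − 1 = 3 at most, or Possible. If the exposure period in the timing factor means the dosing days, 3 − 1 = 2, or Unlikely. An assessor who credited dechallenge for any later recovery would add one factor back.

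Whether Possible counts as drug-related therefore decides much of this endpoint, and the protocol does not say for this endpoint. Elsewhere, for another purpose, section 3(4) refers to events judged related and section 8(3) to events related or probably related.

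**3. How far apart could the two counts be?** Illustration only. Let *p* be the proportion of subjects with any SAE and *f* the share of those with an SAE judged related; both are assumptions. Expected subjects with any SAE = *np*; with a related SAE = *npf*; probability that the counts differ = 1 − (1 − *p*(1 − *f*))^*n*. The protocol gives *n* = 6 to 18; *n* = 9 is three doses of three subjects.

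| *n* | *p* | Any SAE (*np*) | Related SAE, *f* = 0 / 0.25 / 0.5 / 1 | P(counts differ) |
|---|---|---|---|---|
| 6 | 0.10 | 0.6 | 0 / 0.15 / 0.3 / 0.6 | 0.47 / 0.37 / 0.27 / 0 |
| 9 | 0.20 | 1.8 | 0 / 0.45 / 0.9 / 1.8 | 0.87 / 0.77 / 0.61 / 0 |
| 18 | 0.20 | 3.6 | 0 / 0.9 / 1.8 / 3.6 | 0.98 / 0.95 / 0.85 / 0 |
| 18 | 0.40 | 7.2 | 0 / 1.8 / 3.6 / 7.2 | 1.00 / 1.00 / 0.98 / 0 |

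Example: *n* = 18, *p* = 0.20, *f* = 0.5 gives 1 − (1 − 0.10)^18 = 0.85.

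**4. Is the window covered?** Final dose on Day 3 plus 30 days is Day 33. The endpoint runs to Day 90, which leaves 90 − 33 = 57 days outside the monitoring period in sections 4(2), 6 and 8(2). The visit table contradicts them by recording AEs at Day 90. This affects either version of the endpoint.

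**The case against.** A reader might infer more than the documents support, and the case against the stronger readings is sound.

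- **Two rival endpoint definitions.** The synopsis and section 5(2) agree. Section 11(3) is an analysis line and section 13 a list of report contents, which compares nothing. Summarising all SAEs beside a drug-related endpoint would be compatible with that endpoint. The protocol does not say that this is the plan, though, and it gives the endpoint itself no analysis.
- **The main 90-day safety rate.** It is one of three secondary safety endpoints; the primary one is DLT within 14 days.
- **Serious events would be hidden.** Every AE is recorded with its causality grade, and SAEs are reported to the Ethics Committee and sponsor without a causality filter (section 8(5)). Under section 5(1), a symptomatic hemorrhage or an NIHSS rise of 4 or more within 14 days counts as a DLT whatever the attribution, although the synopsis heads the DLT endpoint as related to the product. Deaths count under all-cause mortality. What remains without an endpoint is non-fatal SAEs of any cause over 90 days.
- **Very different numbers.** This depends on *p* and *f*, which the protocol does not give. If every SAE is judged related, the gap is zero.

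It can also be said that a sponsor may choose a related-only endpoint, and that one sentence in section 11(3) would cure the mismatch. That would align the texts, but it would leave the missing cut-off and the dependence on unblinded attribution.

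**Conclusion.** The concern holds as a mismatch between endpoint and analysis, together with a weak endpoint choice. The texts do not show a numerical contradiction. The mismatch rests on reading unqualified SAEs through the protocol's own definitions. The weakness of the filter rests on the scoring rules, the missing cut-off, and the absence of any described control group or blinding. Its direction is toward understating serious harm that looks like a stroke complication.

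The size cannot be computed from the protocol. Under the assumed values, the expected difference runs from 0 subjects (all SAEs judged related) to 3.6 of 18 at an any-SAE rate of 20% with none judged related, or 7.2 of 18 at 40%. It should be corrected before the first subject is dosed, but it does not touch the escalation decision, which rests on DLT.

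**What to change.** 1. In section 5(2) item 1 and the synopsis, make the endpoint the proportion of dosed subjects with at least one SAE, whatever its cause, within 90 days of first dose. Show drug-related SAEs as a subset.
2. State which of the five causality categories count as drug-related for that subset.
3. In section 11(3), name the any-cause SAE proportion in the Safety Analysis Set as the quantity summarised by dose, over the same 90 days, with the related subset beside it.
4. Reconcile the SAE collection window in sections 4(2), 6 and 8(2) with the 90-day endpoint and the visit table.

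**Cost.** Items 1 to 3 change wording only, since seriousness and causality are already recorded for AEs. Item 4 goes further: SAE collection must be confirmed to run to Day 90. That visit already takes place, so the added burden is small. The reported SAE rate will be higher because it includes stroke complications, and the related subset beside it lets readers see the difference.

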1. **Dose Adjustment:** No dose reduction is allowed during the study. If a subject experiences a Grade ≥ 3 AE, study drug administration is suspended until the AE resolves to Grade ≤ 1 ; if the AE is judged to be related to the study drug, the subject withdraws from the study.

2. **Prohibited and Restricted Medications:**

- Prohibited medications: Antineoplastic drugs, immunosuppressants (e.g., cyclosporine, tacrolimus), neurotrophic factors (e.g., nerve growth factor);
- Restricted medications: Antibiotics and antiviral drugs (used only for confirmed infections, with duration documented); non-steroidal anti-inflammatory drugs (NSAIDs) (avoided if possible to reduce bleeding risk).

3. **Concurrent Diseases Management:** If a subject develops a concurrent disease (e.g., pneumonia, myocardial ischemia) during the study, the treating physician provides standard treatment, and the details are documented in the "Concurrent Disease Record Form" in the CRF.
4. **Subject Education:** Subjects are instructed to report any new symptoms (e.g., headache, nasal congestion, rash) to the investigator immediately, and to avoid self-medication with prohibited drugs.

4. Observation Items

(1) Demographic and Clinical Data

1. **Demographic Characteristics:** Gender, age, date of birth, ethnicity, dominant hand, occupation, height, weight, body mass index (BMI);
2. **Clinical History:** Chief complaint, onset time of stroke, detailed history of present illness, primary diagnosis (including infarct location), secondary diagnoses, past medical history (hypertension, diabetes, hyperlipidemia, coronary heart disease), surgical history, allergy history, family history, smoking history (pack-years), drinking history (alcohol consumption per week);
3. **Medication History:** Current medications (including over-the-counter drugs, herbal supplements) at screening, with dosage, frequency, and duration documented.

All data are recorded in the "Baseline Demographic and Clinical Data Form" in the CRF.

(2) Safety Observation Indicators

1. **Vital Signs:** Measured before each dose administration and at each follow-up visit:
 - Pulse (beats per minute), blood pressure (mmHg, measured in the sitting position after 5 minutes of rest), respiratory rate (breaths per minute), body temperature (°C, axillary or oral);
 - Abnormal vital signs (e.g., hypertension: systolic blood pressure ≥ 160 mmHg) are documented and followed up.
2. **Laboratory Tests:**

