- **Grade 1-2 AEs:** Monitor closely; provide symptomatic treatment if needed (e.g., antihistamines for mild rash). Continue study drug administration if the AE is judged to be unrelated or unlikely related to the study drug.
- **Grade 3-4 AEs:** Suspend study drug administration immediately; provide urgent medical treatment (e.g., corticosteroids for severe allergic reactions). The investigator assesses the causal relationship between the AE and the study drug. If the AE is related or probably related, the subject withdraws from the study, and follow-up continues until the AE resolves or stabilizes.
- **SAEs:** Implement the following emergency procedures:
 1. Provide immediate medical treatment to stabilize the subject's condition;
 2. Notify the principal investigator, sponsor, and Ethics Committee within 24 hours of awareness;
 3. Complete the "Serious Adverse Event Report Form" and submit it to the Ethics Committee and sponsor;
 4. Conduct follow-up assessments until the SAE resolves or stabilizes, and submit follow-up reports every 7 days until resolution.

(4) Assessment of Causal Relationship Between Adverse Events and Study Drug

The causal relationship is assessed by the investigator based on the following five factors:

1. **Temporal Relationship:** Whether the AE occurred after administration of the study drug (onset time within the drug exposure period);
2. **Known Pharmacological Effects:** Whether the AE is consistent with the known safety profile of MSC-sEVs (e.g., nasal irritation is a potential local effect);
3. **Decchallenge Response:** Whether the AE resolved or improved after discontinuing the study drug;
4. **Rechallenge Response:** Whether the AE recurred after re-administering the study drug (not applicable in this study due to safety concerns);

5. **Alternative Etiologies:** Whether the AE can be explained by the subject's underlying disease, concurrent medications, or other factors.

The causal relationship is classified into five categories:

- **Definite:** All five factors support a causal relationship;
- **Probable:** Four factors support a causal relationship, and no alternative etiology is identified;
- **Possible:** Three factors support a causal relationship, and alternative etiologies are possible;
- **Unlikely:** Two or fewer factors support a causal relationship, and alternative etiologies are likely;
- **Unrelated:** No factors support a causal relationship, and alternative etiologies are confirmed.

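### The causality count in Section 8(4) includes rechallenge, which the trial rules out, leaves many events in no category, and is never mapped to the relatedness that DLT criterion 1 requires

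*Protocol*

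**What the plan says.** Section 8(4) has the investigator assess causality on five factors: timing, consistency with the known profile, dechallenge, rechallenge and alternative causes. Rechallenge is marked "not applicable in this study due to safety concerns". The category then follows from the number of supporting factors, joined to a clause on alternative causes:

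- Definite: "All five factors support a causal relationship".
- Probable: "Four factors support a causal relationship, and no alternative etiology is identified".
- Possible: three factors, with alternatives possible.
- Unlikely: "Two or fewer factors support a causal relationship, and alternative etiologies are likely".
- Unrelated: no factors, with an alternative confirmed.

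The timing factor carries the gloss "onset time within the drug exposure period", which is not defined. Dosing runs from Day 0 to Day 3 (Section 3(2)); DLTs are assessed over 14 days from the first dose (Section 5(1)).

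The first DLT criterion in Section 5(1) is a "Grade 3-4 AE related to the study drug". The other two, a NIHSS rise of at least 4 points and symptomatic intracranial haemorrhage, carry no causality condition there. The synopsis, however, heads the whole DLT outcome as related to the product.

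Two other places use relatedness, for withdrawal. Section 3(4): "if the AE is judged to be related to the study drug, the subject withdraws from the study". Section 8(3), for Grade 3-4 events: "If the AE is related or probably related, the subject withdraws from the study".

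**The concern.** DLT is the primary endpoint and the only input to the 3+3 escalation rule in Section 1(2). With three subjects per dose, reclassifying one event changes the path. A causality scale with an unreachable top category, gaps in the middle and no stated link to the word *related* leaves criterion 1 without a fixed meaning.

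The direction of the problem matters too. Factor 2 withholds support from a toxicity not yet known for the product, and factor 3 withholds it from one that does not improve. A first dose-escalation study should be most alert to severe events of these kinds, yet the count marks them down.

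**Working it through.** **1. What the count can reach.** Write T, K, D and A for support from timing, known profile, dechallenge and absence of an alternative cause. Rechallenge contributes 0. The maximum is T + K + D + A = 4, below the 5 needed for Definite. Scoring each factor yes or no gives 2^4 = 16 patterns:

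| Factors met | Patterns | Result |
|---|---|---|
| 4 | 1 | Probable |
| 3, being T + K + D | 1 | Possible, if the alternative is a possible one |
| 3, including A | 3 | Possible by count, but the clause on alternatives is not met: no category |
| 2 or fewer | 6 + 4 + 1 = 11 | Unlikely by count; full wording also needs a likely alternative |

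So Possible in its full wording requires T, K and D together.

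**2. Applying both the count and the clause.** Take alternatives at four levels (none, possible, likely, confirmed). This gives 8 × 4 = 32 combinations. Those that fit a category in full: Probable 1, Possible 1, Unlikely 7, Unrelated 1, total 10. The other 32 − 10 = 22 fit none. If a confirmed alternative also satisfies the likely clause, 6 more become Unlikely, leaving 16. If likely and confirmed alternatives also satisfy the possible clause, 2 more become Possible, leaving 14. The gaps survive the generous reading.

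**3. New and non-resolving events, with timely onset (T = 1).**

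| Event | Alternative cause | Count | By count | Full wording |
|---|---|---|---|---|
| New and non-resolving | none | 2 | Unlikely | no category |
| New and non-resolving | possible | 1 | Unlikely | no category |
| New and non-resolving | likely | 1 | Unlikely | Unlikely |
| New only, or non-resolving only | none | 3 | Possible | no category |
| New only, or non-resolving only | possible | 2 | Unlikely | no category |
| New only, or non-resolving only | likely | 2 | Unlikely | Unlikely |

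**4. The protocol's own example.** Section 5(1) names hepatic injury as an instance of criterion 1. Section 8(4) gives only nasal irritation as an example of the known profile. Assume hepatic injury is not in that profile (K = 0) and that a concomitant drug, such as the lipid-lowering therapy in Section 3(2), could explain it (A = 0). With timely onset and full recovery the count is 1 + 0 + 1 + 0 = 2, the Unlikely count.

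**5. Timing.** If the exposure period means the dosing days, which is an assumption, onset on Days 4 to 14 (11 days) also loses T. Dechallenge says little about an event that begins after the last dose, although one that improves still earns the point as worded.

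**6. Effect on escalation (illustration).** Section 1(2) escalates after 0 of 3 DLTs, or after 1 of 3 followed by 0 of 3. Let p be the true DLT rate, s the share of DLTs counted, and q = p × s. Then P(escalate) = (1 − q)^3 + 3q(1 − q)^2 × (1 − q)^3. For p = 0.33:

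- s = 1: q = 0.33, 0.301 + 0.134 = 0.434
- s = 0.75: q = 0.2475, 0.426 + 0.179 = 0.605
- s = 0.5: q = 0.165, 0.582 + 0.201 = 0.783

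| p | s = 1 | s = 0.75 | s = 0.5 | s = 0.25 |
|---|---|---|---|---|
| 0.20 | 0.709 | 0.814 | 0.906 | 0.973 |
| 0.33 | 0.434 | 0.605 | 0.783 | 0.933 |
| 0.50 | 0.172 | 0.351 | 0.600 | 0.862 |

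Both p and s are assumed; the protocol gives neither.

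**The case against.** A reader might infer that any new or any non-resolving toxicity is rated Unlikely at best. The text does not support that. With good timing and no alternative cause, an event with just one of these features has three factors: Possible by count, and no category in full wording. Even the event that is both, with no alternative cause, fails the Unlikely clause and is Unlikely only by count. The scale then leaves the matter to the investigator's judgement, so a systematic push towards unrelated is not shown. This part of the objection stands.

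The claim that every event after Day 3 fails the timing factor also goes too far. The factor asks first whether the event followed administration, and the exposure period is undefined.

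The reach is bounded. In Section 5(1), neurological worsening and symptomatic haemorrhage count without a causality rating. Only the synopsis heading could extend the condition to them.

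The loss under criterion 1 depends on a cut-off that is not stated. The Grade 1-2 rule in Section 8(3) groups unrelated with unlikely, which suggests Possible lies on the related side. The Grade 3-4 rule beside it names related and probably related, which suggests the reverse. The protocol does not settle the question.

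Other safeguards exist: dosing is suspended for Grade 3 or higher events before causality is settled, SAEs are reported within 24 hours whatever their cause, and unexpected severe toxicity can end the study (Section 2(7)). They protect subjects but do not decide what enters the DLT count.

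Lastly, counting patterns equally shows where the wording fails, not how often events will fall there.

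**Conclusion.** Wrong as written. It follows from the text alone that Definite is unreachable, that Probable needs all four usable factors, that Possible in full wording needs T, K and D together, and that 14 to 22 of 32 combinations fit no category, depending on how generously the clauses are read. It also follows that no section maps the five categories to *related*, on which DLT criterion 1 depends. Grade 3-4 events that are both new and non-resolving, or either one with a plausible alternative cause, have the Unlikely count and can be left out of the DLT count. Such alternatives are readily argued in stroke patients on concomitant drugs.

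The conclusion is confined to criterion 1 unless the synopsis heading governs. How many DLTs would be lost cannot be derived from the protocol. The escalation figures show direction and possible scale under assumed p and s, treating all DLTs as arising under criterion 1; a share arising under the other two criteria would bring s closer to 1. The loss of the timing factor after Day 3 holds only if exposure means the dosing days.

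**What to change.** 1. In Section 8(4), remove rechallenge from the count and reset the cut-offs to the applicable factors, so that every pattern falls in exactly one category. Removing rechallenge alone makes the top category reachable but does not help new or non-resolving events.
2. Let known profile and dechallenge raise a rating but not lower it, so that novelty or non-resolution is not scored as evidence against causality.
3. Define the temporal factor to cover the 14-day DLT window.
4. State in Section 5(1) which categories count as related for a DLT, for example all except Unlikely and Unrelated. State whether the synopsis heading imposes relatedness on the other two criteria.
5. Reconcile the relatedness wording of Sections 3(4) and 8(3).

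The cost is protocol wording and a revised adverse event form, with no extra data. The downside is that some events due to the stroke may be counted as DLTs, which errs on the conservative side. The change should be in place before the first subject is dosed.
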